7.13 Plan for Data Management and Statistical Analysis

- Data will be entered by the investigator and resident on duty in the intensive care unit and will be destroyed after the completion of the study, however the results and conclusions will be stored without hampering the subject/ patient's privacy or rights.
- Power of the study is based on the primary outcome which is the change in ONSD following infusion of 20% Mannitol.
- Paired t test, chi square test will be used for data analysis.
- Data will be analysed by using SPSS 20 software version
- The value of $p < 0.05$ will be considered as statistically significant.

7.14 A graphic outline of the study design and procedures using a flow diagram including the timing of assessments.

8. Biases:

Data collection by on duty MD anesthesiology Resident or DM Critical Care Residents will reduce observer and performance bias.

9. Limitation of the study:

- Single centered
- Open label
- No control group

10. Safety considerations:

Regarding the safety concerns during the measurement of optic nerve sheath diameter subjects with ocular injury, glaucoma are being excluded. The acoustic energy used for diagnostic purposes has no described adverse effects. The recent bioeffects and safety report by the American Institute of Ultrasound in Medicine (AIUM) makes no specific mention of the eye. The United States Food and Drug Administration Center for Devices and Radiological Health (US FDA/CDRH) describes an output intensity limit for all eye exposure of 50 mW/cm², recommending the use of a mechanical index (MI) < 0.23, and a thermal index (TI) < 1. The definition of an experienced operator differs, but studies have defined an experienced operator as having performed more than 25 prior transorbital ultrasound examinations.

11. Plan for Supervision and Monitoring:

The research will be continuously supervised by the co-guides [name] [name] and [name] and will be conducted under the guidance of [name].

12. Expected outcome of the Research:

Optic nerve sheath diameter changes are expected to be associated with the administration of 20% Mannitol in patients with raised intracranial pressure. Such an outcome would have various benefits in terms of usefulness of the optic nerve sheath diameter monitoring.

13. Plan for Dissemination of Research:

Research results will be submitted to the Department of Anaesthesiology and Research department, IOM.

Research results will also be submitted for publication in national and international journals of repute.

14. Plan for Utilization of the Research Findings:

The research results would help us in the care of patients in the neurosurgical and neurological intensive care units with non-invasive monitoring.

15. Work Plan

S.N	Activities	2018 AD		2019 AD			
		Nov	Dec	Jan	Feb	Mar	Apr
1	Problem identification						
2	Literature review						
3	Topic selection						
4	Writing thesis proposal						
5	Presentation to sub committee						
6	Review thesis proposal						
7	Submission to IRB						
8	Approval from IRB						
9	Data collection						
10	Data analysis						
11	Final thesis writing						
12	Final correction and submission						

16. Ethical Consideration

Research is based on human optic nerve sheath diameter.

Approval by IRB.

Verbal consent from patients relatives and/or legal guardian would suffice as the study is non-interventional and non-invasive with no effect on patients safety.

Confidentiality will be maintained.

17. Obtaining the Consent

Patients legal guardian will be well counseled and no information will be withheld.

18. Budget

The expenditure during the study will be made by the principal investigator.

Transparent dressing (Tegaderm): 50 pcs: Rs. 2400

Data statistician: Rs. 8000

Stationary: Rs. 4000

Photocopies of proforma and information sheet: Rs.2000

Binding: Rs. 4000

Total: Rs 20400

19. Annexes:

Proforma

“Study on the effect of intravenous administration of 20% Mannitol on the Optic nerve sheath diameter (ONSD) in patients with episodes of raised intracranial pressure.”

Participant serial no.: IP no.: Date:

Name: Age/sex: Weight:

Height: BMI:

Diagnosis: Admission date:

Ventilator parameters at time of baseline measurement

PIP: cmH₂O
PEEP: cmH₂O

Time of 20% Mannitol administration:
Dose of 20% Mannitol administered:
Time of measurement: 30 minutes:
60 minutes:
120 minutes:

MEASURED VARIABLES:

VARIABLES	BASELINE (T ₁)	POST-MANNITOL (30MINUTES: T ₂)	60 MINUTE (T ₃)	120 MINUTES (T ₄)
MEAN ARTERIAL PRESSURE	mmHg	mmHg	mmHg	mmHg
OPTIC NERVE SHEATH DIAMETER	RIGHT: mm	RIGHT: mm	RIGHT: mm	RIGHT: mm
	LEFT: mm	LEFT: mm	LEFT: mm	LEFT: mm
	MEAN: mm	MEAN: mm	MEAN: mm	MEAN: mm
GLASGOW COMA SCALE	E:	E:	E:	E:
	V:	V:	V:	V:
	M:	M:	M:	M:

List of Abbreviations:

ICP	Intracranial pressure
TBI	Traumatic brain injury
SAH	Subarachnoid hemorrhage
ONSD	Optic nerve sheath diameter
CPP	Cerebral perfusion pressure
CBF	Cerebral Blood Flow

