Effect of intravenous administration of 20% Mannitol on the Optic Nerve Sheath Diameter (ONSD) in patients with raised intracranial

pressure.

Approval no: 360(6-11)E²/075/76

Date: 24 Feb, 2019

1. Proposal Title:

Effect of intravenous administration of 20% Mannitol on the Optic Nerve Sheath Diameter (ONSD) in patients with raised intracranial pressure.

2. Project summary:

This is a prospective observational cross-sectional study which will determine the extent of change brought in the optic nerve sheath diameter by the intravenous administration of 20% Mannitol in patients with raised intracranial pressure. The studied patient will be those above the age of 18 years with traumatic brain injury, acute stroke or intracranial hemorrhage, with the features of elevated intracranial pressure as diagnosed by clinical findings, ONSD value > 5 mm and under 20% Mannitol osmotherapy, admitted in the intensive care unit of our institution. Written informed consent will be taken and after the eligibility criteria are met, epidemiological data including age, sex, weight, BMI at the time of admission will be recorded. Measured baseline observational values including optic nerve sheath diameter, mean arterial pressure will also be recorded. Observational variables will be measured after 30 minutes, 60 minutes and 120 minutes following the intravenous administration of 20% Mannitol. The data will be tabulated and analysis performed with SPSS software. The primary outcome will be the change in optic nerve sheath diameter, while the correlation between these variables will also be interpreted.

3. Introduction

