Optic nerve sheath diameter measurement is a common acute care sonographic procedure. Since the change in intracranial pressure is a continuum of event, sonographic monitoring of such an event is possible through optic nerve sheath diameter monitoring. Mannitol is a common drug used in patients/subjects with raised intracranial pressure either due to trauma, subarachnoid haemorrhage or stroke. Its effects on intracranial pressure reduction are well known though the mechanism is not properly understood yet. My study/research aims at studying the pattern and extent of change in the optic nerve sheath diameter after osmotherapy with intravenous 20% Mannitol within its time of peak effect. Monitoring such changes can help tailor the treatment modality and tier according to efficacy. In absence of invasive monitoring in a limited setup like ours and in light of the various complications associated with invasive monitoring, noninvasive monitoring can help us in improving the outcomes in such neurosurgical or neurological cases.

5. Objectives

General:

To study the effect of intravenous administration of 20% Mannitol on the optic nerve sheath diameter in patients with raised intracranial pressure.

Specific:

- To compare the changes in optic nerve sheath diameter brought about by administration of Mannitol within the time of its peak effect.
- To correlate and compare the extent of change in ONSD (Δ ONSD) at 30, 60 and 120 minutes in relation with dose of mannitol administered and change in Mean Arterial Pressure (Δ MAP).
- To correlate the changes in ONSD in relation with PIP and PEEP in patients on Mechanical ventilation.

6. Research Questions/Hypothesis:

Null Hypothesis (H_0): Serial Optic nerve sheath diameter monitoring with a cut-off value of 5.0 mm can reflect changes due to IV administration of 20% Mannitol in patients with raised ICP.

Alternate Hypothesis (H_1): Serial Optic nerve sheath diameter monitoring with a cut-off value of 5.0 mm cannot reflect changes due to IV administration of 20% Mannitol in patients with raised ICP.

Expected outcome: $H_0 \neq H_1$

7. Research Design and Methodology

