7.7 Inclusion and Exclusion Criteria

Inclusion criteria:

- Age > 18 yrs
- Gender: any
- H/o traumatic brain injury/ subarachnoid hemorrhage/ acute stroke
- Mean optic nerve sheath diameter > 5mm (0.5cm)
- Under osmotherapy with 20% Mannitol.

Exclusion criteria:

- Baseline ocular pathology like tumors, Grave's disease and Sarcoidosis
- Previous ocular surgery
- Decompressive cranial surgery

7.8 Study Variables:

Epidemiological variables:

- Age
- Gender
- Weight
- BMI

Measured base line variables:

- GCS score
- Mean arterial pressure
- Optic nerve sheath diameter, T₁ (mean of 3 measurements in each eye)
- Ventilator parameters (PIP and PEEP) in patients on mechanical ventilation.

Measured variables after infusion of 20% Mannitol:

- Dose of 20% mannitol administered
- Mean arterial pressure
- Optic nerve sheath diameter (mean of 3 measurements in each eye) after 30mins(T₂), 60 mins(T₃) and 120 mins(T₄).

7.9 Primary outcomes:

Change in the optic nerve sheath diameter (Δ ONSD) at T₂, T₃ and T₄.

7.10 Secondary outcomes:

- Change in the mean arterial pressure before and after mannitol administration.
- Comparison and correlation between the extent of change in ONSD (Δ ONSD) with dose of mannitol and change in MAP(Δ MAP).
- Correlation between Δ ONSD with PIP and PEEP in mechanically ventilated patients

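### Does section 7.13 have to name a method and a status for the secondary correlations of change in ONSD?

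*Combined protocol and SAP*

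**What the plan says.** Section 7.13 is the whole statistical plan. On tests it says "Paired t test, chi square test will be used for data analysis". The software is SPSS 20, and a p value below 0.05 "will be considered as statistically significant". It also says: "Power of the study is based on the primary outcome which is the change in ONSD following infusion of 20% Mannitol".

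The correlations are announced elsewhere:

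- Section 2 (Project summary) names change in ONSD as the primary outcome and adds "while the correlation between these variables will also be interpreted".
- Section 5, second specific objective, begins "To correlate and compare the extent of change in ONSD (Δ ONSD) at 30, 60 and 120 minutes" and sets this against mannitol dose and change in MAP.
- Section 5, third specific objective: "To correlate the changes in ONSD in relation with PIP and PEEP in patients on Mechanical ventilation".
- Section 7.10 (Secondary outcomes) repeats both, the second as "Correlation between Δ ONSD with PIP and PEEP in mechanically ventilated patients".

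Section 7.9 defines change in ONSD at T2, T3 and T4. Section 7.11 and the proforma record PIP and PEEP at baseline. The proforma's dose line has no printed unit.

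**The concern.** A reader who sets section 5 beside section 7.13 finds objectives with no matching method. The paired t test fits the ONSD change, the MAP change and contrasts between time points. Neither it nor chi-square relates one continuous variable to another. Several choices are left open: the coefficient, which change in ONSD goes with PIP and PEEP, and whether dose means total amount or amount per kg. Chi-square is attached to nothing, and every listed outcome is continuous.

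The p < 0.05 rule is not confined to the primary outcome, and the correlations are nowhere called exploratory. If a dozen are run and each is read at 0.05, a chance association with dose or ventilator pressure could be reported as real. A true weak relation would usually be missed.

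**Working it through.** **1. The plan's own figure.** Section 7.6 uses an effect size of 0.49 (0.24/0.49), two-sided α = 0.05 and 80% power:

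N = (1.96 + 0.84)²/0.49² + 1.96²/2 = 32.65 + 1.92 = 34.57, so 35.

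This matches the stated 35. Exact paired-t power at n = 35 and effect 0.49 is 80.4%. Adding 10% dropout gives 35/0.9 = 38.9, so 39, against the stated 40. The sample size belongs to the paired change and does not depend on the correlations.

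**2. How many correlations.**

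- Explicit in objective 2: dose × 3 times + change in MAP × 3 times = 6.
- PIP and PEEP: objective 3 names no time. One time gives 2 more (total 8). All three times from section 7.9 give 6 more (total 12).

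**3. Chance of at least one p < 0.05 when no relation exists.** For k independent tests this is 1 − 0.95^k, and the expected number of false positives is 0.05k.

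| k | Independent | Simulated, correlated times | Expected false positives |
|---|---|---|---|
| 6 | 26.5% | 16.7-24.9% | 0.3 |
| 8 | 33.7% | 24.1-31.9% | 0.4 |
| 12 | 46.0% | 29.1-42.7% | 0.6 |

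The simulations used 20,000 studies per setting and two-sided Pearson tests. They rest on inputs that are **not in the documents**: 35 patients analysed, 15 to 25 of them ventilated, within-patient correlation across times of 0.5-0.9 for change in ONSD and for change in MAP, and PIP-PEEP correlation of 0 or 0.6. A separate run of 12 tests with all 35 patients in every test gave 46%, 43% and 35% for correlations across times of 0, 0.5 and 0.8.

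**4. Precision.** The |r| detectable with 80% power is tanh(2.8016/√(n − 3)):

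- n = 35: tanh(2.8016/5.657) = 0.46
- n = 40 (no dropout): 0.43
- n = 25, 20, 15 (assumed numbers ventilated): 0.54, 0.59, 0.67

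Power for a true r of 0.3 is about 42% at n = 35 and 19-31% at n = 15 to 25.

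**5. What a change would alter.** Naming Pearson or Spearman leaves every figure in step 3 where it is. A Bonferroni level of 0.05/12 = 0.0042 would reduce the false-positive chance, but would raise the detectable |r| from 0.46 to 0.58 at n = 35 and from 0.59 to 0.72 at n = 20. Calling the correlations exploratory changes no calculation.

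**6. What the plan already settles.** The pairs of variables are named. Objective 2 states its times. PIP and PEEP are taken once, at baseline, and ICU staff are asked to hold the settings unless the treating physician decides otherwise. Weight is recorded, so dose per kg can be derived once the units are written on the form. The correlations sit under secondary outcomes, apart from the primary outcome in section 7.9.

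**The case for a change.** The strongest case for acting is that the gap is real and cheap to close. Correlation is promised in the summary, in two of three specific objectives and in two of three secondary outcomes, and no coefficient appears anywhere. Saying that Pearson is obvious does not settle the dose scale, the time for PIP and PEEP, or whether three readings per patient might be pooled as if independent, which would overstate precision. Secondary is also not the same as exploratory: as written, any correlation with p < 0.05 counts as significant, and the results are meant for journals and for use in ICU care. Even the six explicit tests carry about a 17-25% chance of a false positive. A few lines of text would deal with all of this.

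The facts and the arithmetic stand. The inference to a needed change is weaker. The figure of twelve is one reading, because objective 3 gives no times. Nothing in the plan proposes pooling readings, and objective 2 treats the times separately. No claim of effect from a correlation is planned, and section 9 admits that there is no control group. Whether uncontrolled secondary correlations in a single-centre observational thesis need an exploratory label, a multiplicity adjustment or neither is a point on which statisticians reasonably differ. A rule of Pearson, with Spearman if the plots look skewed, would itself choose the coefficient after seeing the data. Chi-square without a variable is untidy, but gender and diagnosis are recorded categories, and no harm from the spare test has been shown.

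**Conclusion.** No change follows. Section 7.13 leaves out a correlation method and gives chi-square no variable, but this is missing detail that an analyst would fill in the ordinary way. No stated number, power figure or error-rate claim is wrong, and the primary paired comparison with its 35 patients is unaffected.

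The size, if each correlation is read at an unadjusted 0.05, is roughly a 17-25% chance of at least one false positive for the six explicit tests, 24-32% for eight and 29-43% for twelve. These ranges depend on the reading of objective 3 and on the assumed number ventilated and within-patient correlations. They describe the usual limits of unadjusted secondary correlations in a small study. The plan claims neither power nor error control for them, so a reader should take them as descriptive.

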There have been various validated modes of non-invasive ICP monitoring. Trans-cranial Doppler ultrasonography (TCD), optic nerve sheath diameter (ONSD), tympanic membrane displacement and fundoscopic examinations have been proposed as being surrogates to invasive ICP monitoring.^{3,4} There have been many studies comparing the use of invasive against the use of non-invasive modes of ICP monitoring. Among these Optic nerve sheath diameter (ONSD) can be taken as the simplest mode with high positive and negative predictive values on detecting rise in intracranial pressure.⁶ It's correlation with invasively measured intracranial pressure and imaging findings has also been validated⁷ and used extensively in diagnosing episodes of raised intracranial pressure in emergency departments, intensive and neurosurgical units.⁸

The optic nerve is part of the central nervous system and therefore surrounded by the dural sheath. Between the sheath and the white matter is a small 0.1-0.2 mm subarachnoid space which communicates with the intracranial subarachnoid space. In cases with raised intracranial pressure the pressure is also transmitted into this sheath and expansion occurs. This expansion is appreciable via various imaging modalities like CT scans, MRI and ultrasonographic imaging. The feasibility and simplicity of this measurement by ultrasonography has made it a efficient tool in diagnosing and monitoring in acute care setup. The major drawbacks are the inter-observer variation in measurement and conditions that may confound the finding such as tumors, inflammation, grave's disease and sarcoidosis. Change in ONSD measurements performed before and after interventions including hyperventilation, drainage of CSF, administration of Mannitol, tracheal manipulation and lumbar puncture appear to correlate well with the induced change in ICP.^{6,7}

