Launey et. al,¹⁵ performed a study to determine the rate of ONSD variation after Mannitol administration for increased ICP episodes. They included thirteen patients in their study comparing and correlating the changes in ONSD, pulsatility index and invasively monitored ICP. The ONSD significantly decreased after Mannitol infusion from 6.3 to 5.56mm (p=0.0007). Concomitantly the intracranial pressure also decreased for 35(32-41) to 25(22-29)mmHg (p=0.001) and the CPP increased from 47 to 69 (p=0.003). The study concluded that the variations of ONSD appear to be an interesting and effective parameter to evaluate the efficacy of osmotherapy for elevated ICP episodes in patients with acute brain injury/SAH.

A study by Li-juan Wang et al¹⁶ which included 60 patients who underwent measurement of ONSD prior to lumbar puncture on admission and during follow up, concluded that ICP was strongly correlated with ONSD(r=0.758, p<0.001) and this association was independent of all other factors like age, sex, BMI, mean arterial pressure and diastolic blood pressure. It also states that ultrasonographic ONSD measurements provide a potential noninvasive method to quantify ICP that can be conducted at the bedside.

Another study performed in the Indian population by Shirodkar et. al¹⁷ evaluated the efficacy of ONSD by ultrasonography as a non-invasive method for detecting raised intracranial pressure in intensive care unit to compare with CT/MRI findings of raised ICP and to prognosticate ONSD value with treatment. The results showed a sensitivity of detecting raised ICP by ONSD to be 84.6% and a specificity approaching around 99%.

A study by Joushua E Nash et al¹⁸ uses ONSD to diagnose raised ICP along with correlation with CT findings. It also reviews the literature from the past and concludes that <0.50 cm ONSD ensured normal pressure (95% CI 0.469-0.540, p<0.001). The study also quantifies the inter-observer variability in ONSD measurement (0.001-0.002cm). The study also determines the expertise required for measuring ONSD to be around 10-25 case examinations and this has been supported by various other studies.

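### Section 8 claims that on-duty residents reduce observer bias, but readings are unmasked and uncontrolled, so an expectation shift can enter the primary outcome directly

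*Combined protocol and SAP*

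**What the plan says.** Section 8 (Biases) is one sentence: having the anaesthesiology or critical care resident on duty collect the data "will reduce observer and performance bias". It gives no mechanism. Section 7.13 adds "Data will be entered by the investigator and resident on duty in the intensive care unit", so the investigator also handles the data. Section 9 lists open-label conduct and "No control group" as limitations. Section 12 states the expected result: "Optic nerve sheath diameter changes are expected to be associated with the administration of 20% Mannitol".

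The primary outcome (section 7.9) is the within-patient change in ONSD at T2, T3 and T4. Under section 7.11 the diameter is read at the bedside, three times per eye, and averaged. Mannitol then runs over 20 minutes, and readings are repeated 30, 60 and 120 minutes after it ends. The proforma in section 19 has T1 to T4 in adjacent columns on one form, together with the mannitol time and dose, and has no field for the operator.

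On operators, section 3 says of the method "The major drawbacks are the inter-observer variation in measurement", and its literature review reports one study's "inter-observer variability in ONSD measurement (0.001-0.002cm". Section 10 notes that "studies have defined an experienced operator as having performed more than 25 prior transorbital ultrasound examinations" but does not require this of the residents. The text does not mask the operator, assign one operator to each patient, or plan a reliability check or later image reading. The flow diagram could not be read in the copy reviewed.

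**The concern.** An ONSD value depends on where a person places the calipers. Here that person knows the treatment and the time point, can see the baseline, and works to a protocol that says a change is expected. Being on duty alters none of this. If later readings are nudged down, even unintentionally, the paired difference shows a fall that did not occur. In a controlled study with masked readers, a shared reading shift would largely cancel between arms. In this single-arm design nothing cancels it, and the data could not reveal it afterwards.

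A second, smaller issue is that two residents may share the readings of one patient, which would add between-operator variance to the paired difference.

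What is at stake is whether a significant fall can be attributed to a change in the sheath rather than to the reading of it. Section 8 tells the reader that this risk has been reduced.

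**Working it through.** **Inputs.** Section 7.6: mean difference 0.24, SD of differences 0.49 (no unit given; mm assumed), two-sided alpha 0.05, power 80%, 35 evaluable patients and 40 enrolled. Section 7.13: paired t test. Literature review: inter-observer variability 0.001–0.002 cm, which is 0.01–0.02 mm. Section 7.11: 20-minute infusion, last reading 120 minutes after it ends. Bias shifts, operator SDs above 0.02 mm and the frequency of operator change are assumptions, shown as ranges.

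**Step 1. The plan's own figure.** (1.960 + 0.842)² / 0.49² + 1.960² / 2 = 32.69 + 1.92 = 34.6, so 35, as stated. Power of the paired t test at n = 35, from the noncentral t distribution, is 80%.

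**Step 2. Expectation shift, true change zero.** The standard error is 0.49/√35 = 0.0828. The critical t on 34 degrees of freedom is 2.032, so an observed mean change of 2.032 × 0.0828 = 0.17 mm reaches p < 0.05. For a constant shift b in the later readings, the noncentrality is b/0.0828. The chance of a significant result at one time point is then:

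| Assumed shift b (mm) | Share of the planned 0.24 | Noncentrality | Chance of p < 0.05 |
|---|---|---|---|
| 0 | 0% | 0 | 5% |
| 0.02 | 8% | 0.24 | 6% |
| 0.05 | 21% | 0.60 | 9% |
| 0.10 | 42% | 1.21 | 22% |
| 0.15 | 63% | 1.81 | 42% |
| 0.20 | 83% | 2.41 | 65% |

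More patients do not help: at n = 40 the 0.10 mm shift gives 24%. Averaging three readings per eye reduces random error within an operator but leaves a shift common to all three untouched.

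**Step 3. Change of operator within a patient.** Baseline to T4 takes at least 20 + 120 = 140 minutes, so a handover is possible. If a different operator takes the follow-up reading in every patient, the SD of differences becomes √(0.49² + 2s²), where s is the between-operator SD. If only a quarter of patients change operator, the added term is 0.25 × 2s².

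| s (mm) | SD, all change | Power at n = 35 | SD, a quarter change | Power at n = 35 |
|---|---|---|---|---|
| 0.01–0.02 (cited) | 0.490–0.491 | 80% | 0.490 | 80% |
| 0.10 | 0.510 | 77% | 0.495 | 80% |
| 0.20 | 0.566 | 68% | 0.510 | 77% |
| 0.30 | 0.648 | 57% | 0.534 | 73% |

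These losses are upper bounds. The 0.49 is taken from an earlier study and already contains that study's measurement error, which may include some between-operator error.

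**The case against.** Four things can fairly be said for the plan.

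- Open-label conduct and the lack of a control group are disclosed in section 9. That is true, but disclosure does not reduce the bias, and section 8 says the bias is reduced.
- Residents may have less stake in the result than the investigator, which could lessen bias specific to the investigator. This has some force. However, the residents are unmasked too, and the investigator also enters data.
- Measurement is standardised: a fixed depth of 0.3 cm and three averaged readings per eye. That limits random error but not a shared expectation.
- The only inter-observer figure in the protocol is very small. This stands, and it settles the noise question at that value. A reader might infer that rotating residents leave the study seriously underpowered. The documents do not support this: they give no operator SD near 0.1 mm or above and say nothing about shift length or how often operators would change. The introduction calls inter-observer variation a drawback without giving it a size.

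A reader might also infer that the readings will be biased, or that the false-positive rate is 22%. The documents do not support that either. They show that nothing prevents a shift, not that one will occur or how large it would be.

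**Conclusion.** The point holds as a gap between what section 8 claims and what the design does. An expectation shift can enter the paired primary outcome with nothing to mask, cancel or detect it. Its effect ranges from negligible (6% against a nominal 5% at 0.02 mm) to serious (65% at 0.20 mm). That range rests on a constant shift of assumed size, an SD of 0.49 in mm, 35 patients and one time point. Operator change is secondary: it has no visible effect on power at the cited 0.01–0.02 mm, and matters only if the operator SD is about 0.1 mm or more and changes are frequent, both of which are assumptions. It does not follow that an observed fall in ONSD would be an artefact, only that this design could not rule that out. The plan should be changed, and the change is cheap.

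**What to change.** Delete the sentence in section 8 and put the following in its place.

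- Still images are saved at T1 to T4. The primary ONSD values are measured from them later by the existing operator or the investigator, in shuffled order with patient and time labels hidden. The live T1 reading is used only for the entry check at 0.5 cm.
- Each time point is recorded on its own sheet, with an operator ID. Where the rota allows, one operator acquires all four sets in a patient.
- The protocol states that masking covers caliper placement and not image acquisition, so bias is reduced and not removed.

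The masked measurement has to be the required primary value and not an option. A single operator per patient deals with between-operator noise, but that person still remembers T1, and separate sheets do not erase memory.

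Cost: image storage, some rota planning, and up to 40 × 4 × 2 × 3 = 960 caliper readings by existing personnel, for which the budget in section 18 has no line. No additional arm or change in sample size is needed.
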